11. POPULATION PHARMACOKINETIC/ PHARMACODYNAMIC (POPPKPD) ANALYSES

In support of the analysis described below, a specific dataset will be generated for which specifications will be provided in a separate document.

The details of the planned displays are presented in [Appendix 12](#): List of Data Displays.

11.1. Population Pharmacokinetic/Pharmacodynamic Methodology

If deemed appropriate, a population pharmacokinetic/pharmacodynamic analysis will be conducted on the PK population and the ITT population (for blood eosinophils).

For subjects withdrawing prematurely from study treatment, all available data will be included in the analysis.

Zero values for the baseline blood eosinophil count as well as for blood eosinophil count during the study will be replaced by 0.005 prior to log transformation (consistent with approaches used in other analyses).

Outlier data will be assessed for plausibility; however, the aim is to use all available data whenever possible. Any decision to exclude data will be fully documented and specified in the clinical study report.

Blood eosinophil counts were measured during the course of the study over the 52 weeks treatment period and will be analysed by population methods using the most recent population PKPD model (meta-analysis PKPD model of data across indications described in GlaxoSmithKline Document Number [2015N238436_00](#)).

The objectives of the population PKPD analysis are:

- To evaluate mepolizumab pharmacodynamics in subjects with NP following subcutaneous administration of a 100 mg dose every 4 weeks;
- To investigate the impact of covariates of interest in the studied NP population (such as baseline characteristics, co-medication) on specific parameters (e.g. maximum blood eosinophil reduction) in order to identify potential sources of inter-individual variability in these parameters.

Further details are provided in [Appendix 10](#): Pharmacokinetic / Pharmacodynamic Analyses.

12. EXPLORATORY EXPOSURE-EFFICACY RESPONSE ANALYSIS

If deemed appropriate an exposure-efficacy response analysis for the change from baseline in total endoscopic NP score and change from baseline in mean nasal obstruction VAS score during the 52-week study treatment period and subsequent 6-month follow-up period will be conducted.

12.1. Population of Interest

The exploratory exposure-efficacy response analysis will be performed on the ITT population.

12.2. Endpoints

Two measures of exposure will be considered for this analysis:

- i) Dose/bodyweight (Week 52 endpoints only)
- ii) C_{av} = Average concentration defined as $100 \text{ mg} / (\text{post-hoc apparent individual clearance} \times 28\text{d})$

Summary exposures (i) and (ii) will be categorised by quartiles for categorical analysis.

12.3. Methodology

12.3.1. Statistical analysis using exposure quartiles

12.3.1.1. Statistical Methodology Specification

Endpoint / Variables					

 Change from baseline in total endoscopic NP score (based on centrally read data) at Week 52, categorized for analysis as in Section 7.1.5.1. Change from baseline in mean nasal obstruction VAS score during the 4 weeks prior to Week 52, categorized for analysis as in Section 7.1.5.1. 					
Model Specification					

 Each co-primary endpoint will be analyzed using ordinal logistic regression to compare the odds between treatment exposure quartiles to placebo of being in a more favorable endpoint category. Odds ratios will be estimated from the ordinal logistic regression model using the observed marginal distribution of the sample covariates. The analysis model will include the following terms: 
  
 Fixed Categorical:	Region	
 
 Fixed Continuous:	Treatment (placebo and exposure quartiles), Baseline score, Log_e baseline blood eosinophil count	
  
 		Fixed Categorical:	Region	Fixed Continuous:	Treatment (placebo and exposure quartiles), Baseline score, Log_e baseline blood eosinophil count
Fixed Categorical:	Region				
Fixed Continuous:	Treatment (placebo and exposure quartiles), Baseline score, Log_e baseline blood eosinophil count				

• Participants with missing covariate information will be excluded from the analysis
Model Checking & Diagnostics

• Models will be checked for issues with convergence.
Model Results Presentation

• A forest plot of the estimated odds ratio and 95% CI for the comparison of quartiles will be provided.
Subgroup Analyses

• No subgroup analyses are planned for this endpoint
Sensitivity and Supportive Analyses

• No sensitivity/supportive analyses are planned for this endpoint

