1.1. RAP Amendments

Revision chronology:

RAP Section	Amendment Details
Reporting and Analysis Plan_Final: Effective Date 05-SEP-2019	
Reporting and Analysis Plan Amendment 1: Effective Date 20-FEB-2020	
Section 2.1, Section 5.4, Section 7, Section 14.6.5	
 To reflect the changes in protocol amendment 4
Section 12	
 Updated measures of exposure for the exploratory exposure-efficacy response analysis
Section 14.8.1	
 Updated definition for ALT values of potential clinical concern

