7.1.5. Statistical Analyses / Methods

7.1.5.1. Statistical Methodology Specification

Endpoint / Variables

 Change from baseline in total endoscopic NP score (based on centrally read data) at Week 52 Change from baseline in mean nasal obstruction VAS score during the 4 weeks prior to Week 52
Model Specification

 For each co-primary endpoint, the p-value for the difference in median change from baseline

between treatments will be based on the non-parametric Wilcoxon rank-sum test.

- The difference in median change from baseline with 95% confidence intervals will be estimated by quantile regression using a bootstrap approach ([Keene, 2018], [Mehrotra, 2017]). The analysis model will include the following terms:

Fixed Categorical:	Treatment group, Region
Fixed Continuous:	Baseline score, Log _e baseline blood eosinophil count

- Participants with missing covariate information will be excluded from the analysis

Model Checking & Diagnostics

- Models will be checked for issues with convergence.

Model Results Presentation

- Median change from baseline within each treatment group.
- Estimated difference between treatments in median change from baseline with 95% confidence interval (CI).
- p-value comparing treatments groups from the Wilcoxon rank-sum test.
- A cumulative distribution function (CDF) plot will be provided for the change from baseline in endoscopic NP score at Week 52 by treatment group.

Subgroup Analyses

- Section 5.4.2 identifies the subgroups of interest for the co-primary endpoints.

Sensitivity and Supportive Analyses

For sensitivity and supplementary analyses, the same methodology as for the primary efficacy analysis will be used.

Sensitivity analyses

- For the primary analysis the change from baseline value for participants with surgery/sinuplasty or missing data at Week 52 (due to premature withdrawal from the study or another reason) will be based on the worst observed score prior to surgery/sinuplasty or study withdrawal respectively. The following sensitivity analyses will be carried out to examine the potential impact of choices for the handling of subjects with missing data and for the handling of data for subjects undergoing surgery/sinuplasty. Sensitivity analysis will be performed for each co-primary endpoint where:

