7.1.5.1. Statistical Methodology Specification

Endpoint / Variables

Change from baseline in total endoscopic NP score (based on centrally read data) at Week 52 and other defined visits, will be categorized for analysis as follows:
 
 1. \geq 5-point improvement 2. 4-point improvement 3. 3-point improvement 4. 2-point improvement 5. 1-point improvement 6. No change/worsening 7. Nasal surgery prior to visit 
 • For analysis, participants with missing data at Baseline will be included in the 'no change/worsening' category, participants with missing data at a visit will be included in the 'no change/worsening' category for the respective visit. • If a participant had actual surgery prior to a visit, they will be included in the 'Nasal surgery prior to visit' category regardless of whether a score for the respective visit was obtained. 
Change from baseline in mean nasal obstruction VAS score during the 4 weeks prior to Week 52, and other defined 4-week periods, will be categorized for analysis as follows:
 
 1. $>$ 5-point improvement 2. >4 to 5-point improvement 3. >3 to 4-point improvement 4. >2 to 3-point improvement 5. >1 to 2-point improvement 6. >0 to 1-point improvement 7. No change/worsening 8. Nasal surgery prior to visit 
 • For analysis, participants with missing data at Baseline will be included in the 'no change/worsening' category, participants with missing data for the 4-week period will be included in the 'no change/worsening' category for the respective period. • If a participant had actual surgery prior to or during a 4-week period, they will be included in the 'Nasal surgery prior to visit' category regardless of whether data for the respective period was obtained.
Model Specification

 • Each co-primary endpoint will be analyzed using ordinal logistic regression to compare the odds between treatment groups of being in a more favorable endpoint category. • The odds ratio comparing treatment groups will be estimated from the ordinal logistic regression model using the observed marginal distribution of the sample covariates. • The analysis model will include the following terms:

CONFIDENTIAL

205687

Fixed Categorical:	Treatment group, Region
Fixed Continuous:	Baseline score, Log _e baseline blood eosinophil count

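### The exposure-efficacy model lists exposure quartile as a continuous term although it promises quartile-versus-placebo odds ratios, and its response categories are no longer defined

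*SAP*

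**What the plan says.** SAP Section 12 describes an exploratory analysis relating mepolizumab exposure to the two co-primary endpoints, to be done if thought appropriate. Section 12.2 names two exposure measures, dose per body weight and average concentration, and says both will be cut into quartiles for a categorical analysis.

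Section 12.3.1.1 then specifies the model.

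- **Response.** Each endpoint is "categorized for analysis as in Section 7.1.5.1". Section 12 gives no categories of its own.
- **Aim.** Ordinal logistic regression is to "compare the odds between treatment exposure quartiles to placebo of being in a more favorable endpoint category", shown as a forest plot of quartile odds ratios.
- **Terms.** Only region is listed as Fixed Categorical. Under Fixed Continuous comes "Treatment (placebo and exposure quartiles), Baseline score", followed by log baseline eosinophils.

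The current Section 7.1.5.1 specifies a different kind of analysis. The p-value "will be based on the non-parametric Wilcoxon rank-sum test", and "The difference in median change from baseline with 95% confidence intervals will be estimated by quantile regression using a bootstrap approach". It defines no response categories. Those appear only in Section 7.1.5.1 of the superseded plan bound in the same file, where NP-score change "at Week 52 and other defined visits, will be categorized for analysis as follows" (seven levels; eight for nasal obstruction VAS). Section 1.1 of the current plan records one change to Section 12: "Updated measures of exposure for the exploratory exposure-efficacy response analysis".

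**The concern.** There are two separate faults. First, the cross-reference was left behind when Section 7 was rewritten, so the ordinal model has no stated cut-points. Second, the listed form of the exposure term conflicts with the stated aim. A continuous term fits one slope across placebo and the quartiles, forcing equal log-odds steps from placebo to quartile 1, quartile 1 to 2, and so on. It cannot yield four separate quartile-versus-placebo odds ratios.

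The second fault affects the question being asked. The reader of Figures 6.1 to 6.4 wants to know whether response rises with exposure among treated participants. Under a single slope anchored at placebo, a plain drug-placebo difference looks like such a rise.

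**Working it through.** **The plan's own figures.** The documents give no numerical result for this analysis. The design inputs reproduce: for surgery at 40% against 25% with 200 per arm (Protocol 10.1), power = Φ[(0.15 − 1.96 × 0.04684) / 0.04623] = 0.896, against the stated 90%.

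**Inputs.** Allocation is 1:1 with 200 per arm (SAP 2.2, Protocol 10.1), so about 50 participants fall in each mepolizumab quartile. Protocol 10.1 gives one-point improvement rates from the Phase II study:

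- NP score, 27% vs 52%: (0.52/0.48) / (0.27/0.73) = 2.93
- Nasal blockage, 39% vs 70%: (0.70/0.30) / (0.39/0.61) = 3.65

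**Closed-form approximation.** Score placebo x = 0 (weight 0.5) and quartiles x = 1 to 4 (weight 0.125 each). Let the true log odds ratio be δ in every quartile.

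- Mean of x = 0.125 × (1+2+3+4) = 1.25
- Variance = 0.125 × (1+4+9+16) − 1.25² = 3.75 − 1.5625 = 2.1875
- Covariance with the treatment step = δ × (1.25 − 1.25 × 0.5) = 0.625δ
- Slope = 0.625δ / 2.1875 = 0.2857δ

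With δ = 0.7 (OR 2.01, an assumed value) the slope is 0.20, and exp(0.20k) for k = 1 to 4 is 1.22, 1.49, 1.82, 2.23.

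**Maximum-likelihood check.** A proportional-odds model was fitted to expected counts with the same true effect in all four quartiles. Covariates were omitted.

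| True OR in every quartile | Q1 | Q2 | Q3 | Q4 |
|---|---|---|---|---|
| 1.0 (no drug effect) | 1.00 | 1.00 | 1.00 | 1.00 |
| 1.5 | 1.12 | 1.26 | 1.41 | 1.58 |
| 2.0 | 1.22 | 1.48 | 1.80 | 2.19 |
| 2.93 (NP score) | 1.35 | 1.82 | 2.46 | 3.32 |
| 3.65 (VAS) | 1.43 | 2.06 | 2.95 | 4.23 |

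The documents do not give the placebo split over the old categories. Assumed splits, best to worst, were 2, 3, 5, 7, 10, 33, 40% for NP score and 5, 5, 7, 8, 7, 7, 21, 40% for VAS. They match 27% and 39% improvers. The 1.0 row was run for both splits; the 1.5 and 2.0 rows use the NP split.

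With a five-level categorical term the same data return 2.93 in every quartile for NP score and 3.65 in every quartile for VAS.

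**Simulation.** In 300 simulated trials per endpoint with a flat effect, the linear slope was positive and significant in all of them. A test for differences between quartiles rejected in 5.7% (NP score) and 9.0% (VAS). The slope is detecting drug against placebo, not exposure.

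**The missing categories.** Reinstating the old list does not settle the response. The superseded plan gave actual surgery its own worst level and placed missing data with no change or worsening. Current Sections 7.1.1 and 14.6.5 instead assign the worst observed value for surgery/sinuplasty and for missing data. Because 14.6.5 searches from baseline onward, an assigned value cannot show improvement. These participants would therefore join the no-change/worsening level unless a separate level is kept. At the planning rates that choice concerns 0.40 × 200 = 80 placebo and 0.25 × 200 = 50 mepolizumab participants with surgery.

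**The case against.** The strongest reply is that nobody would code the term linearly. The heading of 12.3.1, the categorical wording in 12.2, the quartile-versus-placebo aim and the forest plot all call for groups. Where the SAP puts a grouped count under Fixed Continuous, as with previous surgeries in 7.2.1.4, it labels it ordinal; the exposure term has no such label and no scores. A misplaced table entry is the likelier explanation. That stands, and it makes this an internal contradiction rather than a settled plan to fit a biased model. The written specification still says continuous, the superseded plan's 12.3.1.1 has the same entry, and the models that compare the two arms list treatment group as categorical.

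A reader might also infer four stronger things that the documents do not support.

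- *The model shows a gradient whatever the truth.* It does not: with no drug effect every odds ratio is 1.00.
- *Surgery and missing data have no rule.* They do, in 7.1.1 and 14.6.5. What is missing is the cut-points and whether surgery keeps its own level.
- *Nothing can be run.* NP-score change is already an ordered integer scale, so a proportional-odds model could use it directly. The VAS mean does need cut-points if it is to be categorised.
- *The co-primary quantile regression must replace the ordinal model.* An exploratory analysis need not follow the primary method, and with about 50 per quartile, medians of an integer score may be too coarse to show a gradient.

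**Conclusion.** The point holds as a contradiction plus a dead reference, both in SAP 12.3.1.1. The undefined response holds however exposure is coded. The false gradient rests on two conditions: the term is coded 0 to 4 as listed, and mepolizumab truly differs from placebo by a similar amount in each quartile. Under both, the apparent odds ratio of quartile 4 to quartile 1 is about 1.8 for a flat effect near 2.0 (2.23/1.22) and about 2.5 for a flat effect of 2.93 (3.32/1.35), where the truth is 1. The exact figures depend on the assumed placebo split and omit covariates, but the rising pattern appears at every non-null effect tried.

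The consequence is small. The analysis is exploratory and conditional, delivered as figures after the main statistical reporting, and outside the testing hierarchy of Section 5.5. No co-primary or secondary conclusion is affected.

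**What to change.** In SAP 12.3.1.1:

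1. Move exposure group to Fixed Categorical as a five-level term (placebo, quartiles 1 to 4), keep the other covariates, and report four odds ratios against placebo with 95% confidence intervals.
2. Replace the cross-reference to 7.1.5.1 with the NP-score and nasal obstruction VAS categories written out in Section 12. Apply them to the worst-observed-score data of 7.1.1 and 14.6.5, and state whether surgery/sinuplasty keeps its own worst category.
3. Point Figures 2.1 and 2.5 in Section 14.12.7 to the same list, since they also call for percentages by category.

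Using the co-primary quantile regression with the five-level term instead is an acceptable option, not a requirement.

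The cost is SAP wording, with no new data. The categorical term uses three more parameters than a slope and rests on about 50 participants per quartile, so individual intervals will be wider; that is the price of estimating what the section promises.

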**Treatment Groups and Duration:**

The currently marketed drug product, Nucala (mepolizumab), is supplied as a 100 mg single-dose vial containing a sterile, preservative-free, lyophilized powder for reconstitution and SC injection.

A liquid formulation of mepolizumab is under development which will be provided as pre-filled syringes in a safety syringe device for this study. The liquid formulation in a safety syringe device must be administered by a health care professional in this study. There will also be a matched safety syringe with placebo.

Participants who are successfully enrolled into the study will be randomized into one of two treatment groups, receiving a total of thirteen doses (one every four weeks):

- Group 1: 100 mg SC of mepolizumab on top of SoC which includes intranasal MF
- Group 2: Placebo SC on top of SoC which includes intranasal MF

A participant is considered to have completed study treatment if he/she attends study Visit 15 (Week 52).

For up to the first 200 randomized participants, the final study visit will be Week 76 (Visit 18). For the remainder of participants who are not participating in the 6 months no treatment follow up, the final study visit will be Week 52 (Visit 15).

The end of the whole study is defined as the date of the last visit of the last participant in the study or last scheduled procedure shown in the SoA for the last participant in the trial globally.

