**2. SCHEDULE OF ACTIVITIES (SOA)**

		Pre screen 	Screening 	Treatment Phase			No treatment Follow 		
Visit		0	1	2	3 -14	15	16-17	18	EW Visit
Study day (Visit window $\pm$ 7 days)	Procedure		(28 days prior to Day 1)	1	29, 57, 85, 113, 141, 169, 197, 225, 253, 281, 309, 337	365	421, 477	533	28 days post last visit
Week				0	4, 8, 12, 16, 20, 24, 28, 32, 36, 40, 44, 48	52	60, 68	76	
Screening/ baseline	Informed consent 	X							
	Concurrent medication review (including INCS)	X	X						
	Inclusion and exclusion criteria		X						
	Demography	X							
	Full physical exam including height and weight		X						
	Medical history (including past and present medical conditions, substance usage family history of premature CV disease) and asthma exacerbation		X						
	History of HIV and Hep B and Hep C screen		X						
	Parasitic screening 		X						
	Medication History including INCS and OCS use for NP		X						
	History of NP surgery		X						
Screening 12-lead ECG		X							

	Procedure	Pre screen 	Screening 	Treatment Phase			No treatment Follow 		
Visit		0	1	2	3 -14	15	16-17	18	EW Visit
Study day (Visit window ± 7 days)			(28 days prior to Day 1)	1	29, 57, 85, 113, 141, 169, 197, 225, 253, 281, 309, 337	365	421, 477	533	28 days post last visit
Week				0	4, 8, 12, 16, 20, 24, 28, 32, 36, 40, 44, 48	52	60, 68	76	
	Screening Vital signs		X						
	Dispense "Medical Problems and Medication Taken Worksheet"	X	X						
	Collect "Medical Problems and Medication Taken Worksheet"		X						
	SAE review		X						
	Assessment of endoscopic NP score		X						
	Overall VAS symptom score and VAS for nasal obstruction to be captured on eDiary after training		X						
	Screening Laboratory assessments (include liver chemistries)		X						
	Screening Urinalysis		X						
	Urine pregnancy test (WOCBP only)		X						
	Dispense MF and eDiary		X						
	Register visit	X	X	X	X	X	X	X	X
	Review randomisation criteria			X					

		Pre screen 	Screening 	Treatment Phase			No treatment Follow 		
Visit		0	1	2	3 -14	15	16-17	18	EW Visit
Study day (Visit window ± 7 days)	Procedure		(28 days prior to Day 1)	1	29, 57, 85, 113, 141, 169, 197, 225, 253, 281, 309, 337	365	421, 477	533	28 days post last visit
Week				0	4, 8, 12, 16, 20, 24, 28, 32, 36, 40, 44, 48	52	60, 68	76	
	Randomisation (if applicable)			X					
	Genetic sample (PGX)				X				

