14.9.2.1. Base Model

In consideration of the sparse sampling (3 samples post-start of treatment over 68 weeks: Week 4, 52 and 68) and the wealth of mepolizumab PK knowledge, the most recent population PK model will be applied directly to the dataset without estimation (e.g. $\text{maxevals}=0$ in NONMEM) and predictions generated, against which the model will be validated prospectively using appropriate goodness of fit tests. For example, the Anderson-Darling and Cramér-von Mises tests are accepted methods of comparing Empirical Distribution Functions for model and data (i.e. PK concentrations) to evaluate whether independent observations (i.e. observed PK concentrations from the study) are adequately described by a model (i.e. most recent population PK model).

The following will be obtained:

- A description of the key models tested during the model development will be provided and tabulated;
- Population mepolizumab plasma PK parameter estimates with 95% CI from the final model will be tabulated. Goodness of fit plots for the final model will be presented;
- Individual post-hoc PK parameter estimates (such as area under the plasma concentration-time curve over the dosing interval $[AUC(0-\tau)]$, $C_{AV} [AUC(0-\tau)/\tau]$) will be summarised descriptively and listed;
- Individual post-hoc predicted plasma concentrations will be summarised descriptively and listed;
- Accumulation ratio estimate will be assessed at Week 52.

The most recent model consists of a two-compartment pharmacokinetic model with first-order absorption and elimination. Bodyweight is incorporated into the model using allometry with fixed physiological allometric exponents of 0.75 and unity for clearance and volumes, respectively. Albumin and creatinine clearance are also included as covariates of mepolizumab clearance on physiological grounds, however their effects are small and not of clinical relevance. Details of the model can be found in report GlaxoSmithKline Document Number [2015N238436_00](#).

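### The dose/bodyweight exposure quartiles are bodyweight groups set against undivided placebo without adjustment for weight, so their odds ratios mix the drug effect with any prognostic effect of weight

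*SAP*

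**What the plan says.** References are to the current SAP (RAP Amendment 1).

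- **Dose.** The protocol synopsis gives one active regimen: "Group 1: 100 mg SC of mepolizumab on top of SoC which includes intranasal MF".
- **Exposure measures.** SAP 12.2 names two: (i) dose divided by bodyweight, and (ii) Cav, which is 100 mg over post-hoc individual clearance times 28 days. "Summary exposures (i) and (ii) will be categorised by quartiles for categorical analysis".
- **Comparison.** SAP 12.3.1.1 uses "ordinal logistic regression to compare the odds between treatment exposure quartiles to placebo of being in a more favorable endpoint category".
- **Model terms.** These are "Treatment (placebo and exposure quartiles), Baseline score", log baseline eosinophil count and region. The treatment term is listed among the continuous terms; it is read here as a five-level factor with a single placebo level. Bodyweight is not a covariate.
- **Supportive work.** "No sensitivity/supportive analyses are planned for this endpoint".
- **Display.** A forest plot of the quartile odds ratios with 95% confidence intervals. SAP 14.12.14 lists Figures 6.1 and 6.3 for dose/bodyweight, and 6.2 and 6.4 for Cav.
- **Weight data.** The protocol's Schedule of Activities has "Full physical exam including height and weight" at Visit 1, before randomisation, so weight is available in both arms.

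**The concern.** An exposure-response display should show whether the drug effect differs by exposure. With a constant 100 mg numerator, ranking participants by 100/weight is ranking them by weight in reverse: the top exposure quartile is the lightest quarter of the mepolizumab arm and the bottom quartile is the heaviest.

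Randomisation makes weight comparable between whole arms. It does not make a weight-selected quarter of one arm comparable with all of the other. Each quartile odds ratio therefore contains the drug effect and the prognostic difference between that weight band and the average placebo participant. Within the mepolizumab arm, exposure (i) and weight are the same variable, so only the placebo data can separate the two. The plan has those data but does not use them for this.

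If heavier participants do worse for reasons unrelated to the drug, a flat drug effect looks like a rising exposure-response. If they do better, a true rising response is flattened or reversed. Cav shares part of the problem because, in SAP 14.9.2.1, "Bodyweight is incorporated into the model using allometry", with an exponent of 0.75 on clearance.

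**Working it through.** The plan gives no figure for this analysis, so the check is of direction and size.

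**Inputs from the documents.** 200 per arm and NP-score one-point improvement in 27% against 52% (Protocol 10.1). These rates give about 99.9% power for a two-proportion comparison at 200 per arm, consistent with the stated power of over 90%. The implied odds ratio is (0.52/0.48)/(0.27/0.73) = 2.93, used here as a drug effect that is the same at every weight.

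**Assumptions.** Log weight is normal with the same distribution in both arms. The placebo response falls in seven ordered categories with 25, 48, 14, 7, 4, 1.5 and 0.5%, worst to best (the last five sum to 27%). The prognostic effect is an odds ratio g per SD of heavier weight, varied because the documents give none. Region, baseline score and eosinophils were left out, so g must be read as the effect of weight remaining after those terms.

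**Hand calculation.** The mean of a standard normal within its quartiles is ±1.271 (outer) and ±0.325 (inner). Against pooled placebo, whose mean is 0, the quartile odds ratio is roughly 2.93 × exp(ln g × quartile mean). For g = 0.80, ln g = −0.223:

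- heaviest: 2.93 × exp(−0.284) = 2.21
- second: 2.93 × exp(−0.073) = 2.73
- third: 2.93 × exp(0.073) = 3.15
- lightest: 2.93 × exp(0.284) = 3.89

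**Simulation, planned model** (proportional odds, 30,000 per arm, true odds ratio 2.93 in every quartile):

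| g per SD | Heaviest | 2nd | 3rd | Lightest |
|---|---|---|---|---|
| 1.00 | 2.95 | 2.95 | 2.88 | 2.85 |
| 0.80 | 2.22 | 2.74 | 3.09 | 3.82 |
| 0.67 | 1.76 | 2.55 | 3.22 | 4.71 |
| 0.50 | 1.22 | 2.26 | 3.40 | 6.45 |

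The g = 0.80 row agrees with the hand calculation. The lower rows are strong effects, shown only to bound the range.

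**Weak effects.** For g = 0.95 the same formula gives about 2.93 × exp(∓0.065), or 2.7 to 3.1. In a separate simulation (200 per arm, true odds ratio 2.5, 300 trials), a correlation of 0.05 between log weight and the latent response left the heaviest quartile's 95% interval covering the truth in 93% of trials. With logistic error SD π/√3 = 1.814, that correlation is exp(−0.0501 × 1.814) = 0.91 per SD.

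**With log bodyweight added,** the quartile odds ratios are 2.86 to 2.99 in all four scenarios. Comparing mepolizumab with placebo inside the same weight quartile gives 2.78 to 3.04.

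**The case against.** The strongest reply is that the premise is unsupported. No section says weight predicts polyp score or obstruction. It is in none of the efficacy covariate lists (SAP 5.4.1) or subgroups (5.4.2) and enters only as a PK covariate. Any effect of weight acting through baseline severity, eosinophils or region would be at least partly adjusted away. If nothing remains, the planned display is sound. This stands: it makes the point conditional and limits its size. It does not remove the mechanism, and the plan has no step that would show whether the condition holds.

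Three stronger readings go beyond the documents:

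- **An inflated false-positive rate.** In simulated trials of 200 per arm with g = 0.80, a linear trend across quartiles reached p<0.05 in 42%. The SAP plans no such test, only a forest plot. At a correlation of 0.1 (about 0.83 per SD), the intervals for the heaviest and lightest quartiles overlapped in 96% of trials, so at that strength the plot would rarely show clear separation.
- **Evidence about dosing in heavier patients.** SAP 12 states no such purpose. The analysis is exploratory, run at discretion and delivered after the main reporting.
- **Equal confounding of Cav.** Individual clearance also reflects albumin, creatinine clearance and individual deviation, so only part of the Cav ranking is weight. Cav was not simulated.

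**Conclusion.** The point holds for dose/bodyweight as a conditional one. As written, the quartile odds ratios are free of this bias only if weight has no prognostic effect beyond region, baseline score and log eosinophils. At an assumed odds ratio of 0.80 per SD of heavier weight, a flat effect of 2.93 would be displayed as about 2.2 to 3.8; with no effect the bias is zero, and near 0.95 per SD it is small. If heavier participants do better, the distortion runs the other way. For Cav the problem is the same in kind but partial.

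A reader might infer that the trial's efficacy conclusions are at risk. They are not: the analysis is outside the testing hierarchy in SAP 5.5, and no primary or secondary result depends on it. This is a low-cost improvement to an exploratory display.

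**What to change.** In SAP 12.3.1.1, add log baseline bodyweight (Visit 1, recorded in both arms) as a continuous covariate for both exposure measures. For Cav this deals only with the part of the confounding that comes through weight.

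Optionally, for dose/bodyweight, add a supportive display: place placebo participants in the same bodyweight bands and plot mepolizumab against placebo within each band. This avoids assuming that the effect of weight is linear on the log scale.

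The cost is a sentence of SAP text and a line or two of code, with no new data. In the separate simulation (true odds ratio 2.5), the mean standard error of the quartile log odds ratios rose from 0.281 to about 0.301 with the covariate (0.301/0.281 = 1.07, or 7%). It rose to 0.359 with placebo split by weight (0.359/0.281 = 1.28, or 28%), which is why the covariate is preferred as the main analysis.
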